Thalassemia is the most common hereditary disorder, with a global prevalence of 18.28 26 27 per 100,000 people [1]. In Thailand, approximately 1% of the population is affected by this condition [2]. The pathogenesis of thalassemia arises from defective globin chain production, 28 which is regulated by alpha- and beta-globin genes. This results in reduced or absent synthesis of 29 globin chains, leading to clinical manifestations such as anemia, jaundice, hepatosplenomegaly, 30 31 and growth retardation. The clinical symptoms and severity of thalassemia are categorized into two groups based on the necessity of blood transfusions: transfusion-dependent thalassemia (TDT) 32 and non-transfusion-dependent thalassemia (NTDT) patients [3]. Accordingly, TDT patients 33 develop iron overload due to regular blood transfusions with approximately 0.8 mg of iron per 1 34 mL of transfused blood [4] along with the lack of an effective iron excretion mechanism in the 35 body [5]. In comparison, iron overload in NTDT patients mostly results from increased intestinal 36 37 iron absorption and ineffective erythropoiesis of which chronic hypoxia leads to an increased erythroferrone (ERFE) secretion, suppressed hepcidin production and enhanced intestinal iron 38 absorption [6-8]. Although iron overload in NTDT patients does not significantly increase 39 mortality due to cardiac iron deposition [9-12], it poses risks for hormone deficiencies, 40 osteoporosis, pulmonary hypertension, and liver disease, which is a leading cause of death [13-41 15]. Among the mechanisms contributing to iron overload, one critical pathway involves increased 42 43 intestinal absorption of dietary iron which is 90% non-heme and 10% heme iron. Non-heme iron absorption requires conversion to ferrous iron, mediated by gastric enzymes and an acidic 44 environment [16]. Therefore, agents/compounds that reduce gastric acidity may decrease iron 45 absorption are relevant. 46

Proton pump inhibitors (PPIs), widely used to reduce gastric acid, inhibit the proton-47 potassium ATPase in parietal cells at the final step in gastric acid secretion, thereby reducing 48 49 gastric acidity [17]. Lower gastric acidity may be insufficient to solubilize dietary iron, interfere with intestinal iron absorption and potentially induce iron deficiency [18, 19]. Previous studies 50 have demonstrated the use of PPIs, including pantoprazole and esomeprazole, in managing iron 51 overload in thalassemia patients and observed a reduction in systemic iron accumulation [20-23]. 52 Additionally, dietary factors such as calcium-rich foods and polyphenols can reduce iron 53 absorption [24]. Resveratrol that is an antioxidative polyphenolic compound [25, 26] can reduce 54 oxidative stress, improve hepatic iron-overload states [27, 28], decrease intestinal iron absorption 55 56 [29] and increase fetal hemoglobin (HbF) levels in beta-thalassemia patients [30].

57 Nowadays, the standard treatment for iron overload in thalassemia involves iron chelation 58 therapy which standard iron chelators including deferasirox (DFX), deferiprone (DFP) and 59 deferoxamine (DFO) are used in Thailand. However, parenteral administration of DFO, limited accessibility to DFX, and severe side effects or suboptimal outcomes with DFP may hinder effective management in NTDT patients with iron overload. Given these limitations and the underlying mechanisms of iron overload, this study aims to investigate the effects of omeprazole as PPI and resveratrol as an adjuvant on dietary iron absorption in NTDT patients. We hypothesize that these interventions could further reduce systemic iron levels through their proposed mechanisms.

66

67 **Research Hypothesis**

68 69

70 71 Adjunctive omeprazole or resveratrol in combination with iron chelators could reduce serum ferritin compared with placebo.

- 72 Study Goals and Objectives
- 73

77

74 Primary Objective

To evaluate the efficacy of adjunct omeprazole or resveratrol in combination with iron
 chelators in reducing serum ferritin compared to placebo

- 78 Secondary Objectives
- 1. To evaluate the efficacy of adjunct omeprazole or resveratrol in combination with iron
 chelators in reducing labile plasma iron (LPI), non-transferrin bound iron (NTBI) and serum iron
 (SI) compared to placebo

2. To study the association between adjunct omeprazole or resveratrol in combination with
 iron chelators and the levels of ERFE and hepcidin (Hcd)

- 3. To study the association between resveratrol and changes in HbF levels
- 84 85
- 4. To assess the adverse effects of adjunct omeprazole or resveratrol with iron chelators
- 86

87 Ethics

88 This study has been approved by the Human Experimentation Committee Research Institute for Health Sciences and authorized by Associate [name], Ph.D., a 89 90 Chairman of the Committee, Faculty of Medicine, Chiang Mai University, Chiang Mai 50200, Thailand, Certificate Number: 476/2024 (English version) and 476/2567 (Thai version), Date: 17th 91 92 December 2024. Adherence to ethical guidelines was of prime importance throughout the study process. All patients will be fully informed about the particulars of the study and willingly provide 93 94 their signatures on the consent forms before any study procedures are performed. This study 95 follows the guidelines of the Helsinki Declaration 2008, revised in 2013: Ethical Principles for Medical Research Involving Human Subjects. Subjects' rights have been protected by an 96 appropriate Institutional Review Board and written informed consent will be granted from all 97 98 subjects.

99

100 Methods

- 101
- 102 Study Design
- 103 Phase 3, randomized, double-blind, placebo-controlled trial
- 104

105 Scope of Research

Non-transfusion thalassemia patients with secondary iron overload visiting Out-patient
 department numbers 9 or 23 at the Division of Hematology, Department of Internal Medicine,
 Faculty of Medicine, Chiang Mai University, Chiang Mai, Thailand between 10th February 2025
 and 30th April 2026.

110 111

Study Population

112

113 Inclusion Criteria

- 114 Age 20-65 years
- 115 Non-transfusion dependent thalassemia [alpha or beta] diagnosis by HPLC, PCR or gene 116 mutation
- Hemochromatosis with serum ferritin 300-1000 ng/mL or > 1000 ng/mL with maximum
 iron chelator (DFP at 75 mg/kg/day or DFX at 20 mg/kg/day)
- Concurrent iron chelators without changing dose during 3 months before enrollment and
 no tendency to adjust the dose of iron chelators between study
- 121 Inform consent
- 122

123 Exclusion Criteria

- 124 Pregnancy or breastfeeding
- Chronic inflammation or other conditions that might confound serum ferritin
 interpretation
- Alanine transaminase more than 5 times upper limited of normal, creatinine clearance < 60 mL/min
- 129 Can not receive oral medication
- 130 Currently receive omeprazole or resveratrol
- 131 allergy to omeprazole or resveratrol
- 132

133 Discontinuation Criteria

- Have more or equal than grade 3 adverse events
- 135 Have conditions that are not suitable for continuation of study
- 136 Protocol violations that significantly affect data collection or interpretation
- 137 Pregnancy
- 138 Need to increase the dose of iron chelation while currently in study
- 139 Have indication for proton pump inhibitor or resveratrol such as gastrointestinal bleeding
- 140 Withdrawal of informed consent
- 141
- 142 Sample Size Calculation
- Expected standardized difference of 0.22 from the Eghbali et al. [22] study which found that adjunct pantoprazole with iron chelators could lower serum ferritin more than iron chelators alone by decreasing serum ferritin from 1444 ± 613 ng/mL to 1197 ± 956 ng/mL and 1928 ± 694 ng/mL to 1501 ± 385 ng/mL respectively. If alpha = 0.05 and beta = 0.2, the estimated sample size is 20 persons in each study group [31] as shown in Table 1.
- **Table 1** Estimated stepped rules of thumb for required trial sample size/treatment arm [31].

Standard difference	80% powered main trial	90% powered main trial
Extra small ($\delta < 0.1$)	50	75
Small $(0.1 \le \delta < 0.3)$	20	25
Medium $(0.3 \le \delta < 0.7)$	10	15
Large ($\delta \ge 0.7$)	10	10

149

150 Study Intervention

- Divide the patients into three study groups in a 1:1:1 ratio using stratified randomization
 based on gender (male and female) and serum ferritin (<1,000, equal to 1,000 or >1,000
 ng/mL). The randomization will be used web-based randomization.
- Allocation concealment will use sealed envelopes to ensure concealment, A staff member not involved in this study will place the study drugs into opaque, sealed envelopes and label them into unique codes. The patients will receive the study drug corresponding to the code on their envelope, without knowing the content. The code lists will be securely stored and remain inaccessible to the research team during the trial.
- This study will use a double-blind technique for patients and outcome assessors. Three study compounds including omeprazole, resveratrol and placebo will be prepared and filled in gelatin capsules with the same appearance as follows; 20 mg omeprazole capsule, 250 mg resveratrol capsule and 20 mg maltodextrin. The capsules will be packed in a white plastic bottle (30 capsules each) and labeled codes under the bottles.
- The patients in Group 1 will take an omeprazole capsule orally twice daily (total 40 mg/day) in the morning and evening before meal for 6 months.
- The patients in Group 2 will take a resveratrol capsule orally twice daily (total 500 mg/day)
 in the morning and evening before meal for 6 months.
- The patients in Group 3 will take a placebo capsule orally twice daily in the morning and evening before meal for 6 months.
- All groups will receive standard treatments including iron chelators, folic acid
 supplementation, vitamin D supplementation, calcium supplementation and lifestyle
 modifications throughout the study.

Research Design

 - The patients will be appointed at the first visit, 3 months and 6 months to evaluate clinical signs, blood parameters and side-effects. If there are side effects more or equal to grade 3, the doctors may decrease the dosage of the study drug according to the following table.

	Side effects	Dose	adjustmen	t	
	Grade \geq 3 Nausea, vomiting, diarrhea, bloating	Decreased study drug 1 lev daily dose]	vel [from tw	vice daily do	ose to once
3	- In each visit, the patients will be requested to collect their blood (30 mL) which will be				hich will be
)	separated into EDTA-whole blood (5 mL) and clotted blood (25 mL). Whole blood will be				
)	used for complete blood count (CBC) analysis and Hb typing. Clotted blood will be				
	separated into the serum to be used for quantitation of kidney function biomarkers such as				kers such as
2	blood urea nitrogen (BUN) and creatinine (Cr); electrolytes (e.g., Na ⁺ , K ⁺ , Ca ²⁺ , Mg ²⁺ and			$^{2+}$, Mg ²⁺ and	
3	phosphates); liver function biomarkers such as aspartate aminotransferase (AST), alanine				
ŀ	aminotransferase (ALT) and alkaline phosphatase (ALP); and iron parameters such as				
5	serum ferritin (sFt, SI), total iron-binding capacity (TIBC), NTBI, LPI, Hcd and ERFE			l and ERFE	
6	according to the below table.				
			at at 14	and	and

Activities	1 st visit	2 nd visit	3 rd visit
History taking and physical examination			

Blood for CBC, BUN, Cr, electrolytes, AST, ALT, ALP, sFt, %TS, TIBC, SI, Hb typing, LPI, NTBI, Hcd and ERFE		
Blood for quantitation of serum vitamin B12, vitamin D, Ca^{2+} and Mg^{2+} , and determination of Hb type		
Adverse effect record		

187

188 Laboratory Investigation

- 1) CBC will be analyzed using an automated Beckman Cell Analyzer machine according to the
 manufacturer's instruction at the Central Laboratory, Maharaj Nakorn Chiang Mai Hospital,
 Faculty of Medicine, Chiang Mai University.
- 192 2) Hb typing will be performed at the Hematology laboratory, Department of Internal Medicine,193 Chiang Mai University.
- 3) Serum BUN, Cr, electrolytes, AST, ALT, ALP, sFt, SI and TIBC will be quantified using an
 automated Roche Cobus Biochemical Analyzer machine according to the manufacturer's
 instruction at the Central Laboratory, Maharaj Nakorn Chiang Mai Hospital, Faculty of
 Medicine, Chiang Mai University.
- 4) Serum iron parameters will be quantified at the Oxidative Stress Laboratory, Department of
 Biochemistry, Faculty of Medicine, Chiang Mai University using specific reagents and
 techniques as described below.
- 4.1) LPI using rhodamine B fluorescence probe [32]
- 4.2) NTBI using NTA chelation/iron chelator fluorescence beads/flow cytometry [32]
- 4.3) Hcd using a sandwich ELISA kit (ABBEXA limited company, Cambridge, UK)
 according to the manufacturer's instruction [33]
- 4.4) ERFE using a sandwich ELISA kit (ABBEXA limited company, Cambridge, UK)
 according to the manufacturer's instruction [34]

208 Statistical Analysis

207

All patients who receive at least 1-time study drug will be analyzed in an Intention-to-treat 209 210 analysis. Patients who receive at least 80% of the study drug will be analyzed in a Per-protocol analysis. Descriptive statistics will be used for the analysis of demographic data. Primary outcome 211 and secondary outcomes [continuous variable] will be analyzed using Friedman's analysis of 212 variance (ANOVA) test. Secondary outcomes [dichotomous variable] will be analyzed using Chi-213 square or Fisher exact test for independent data or Cochran's Q test for dependent data. The 214 association between continuous variables will be analyzed using Pearson's or Spearman's test. 215 216 Accordingly, a P-value <0.05 is considered statistical significance.

217 Duration of Study Plan

```
219
```

References 220

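### The HbF objective and its analysis pool alpha- and beta-thalassemia patients with no account of type, although the protocol's only HbF rationale is in beta-thalassemia; this may dilute the effect

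*Protocol*

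**What the plan says.** - **Rationale (introduction).** Resveratrol is said to "increase fetal hemoglobin (HbF) levels in beta-thalassemia patients". No HbF effect in alpha-thalassemia is claimed or denied.
- **Eligibility (Inclusion Criteria).** "Non-transfusion dependent thalassemia [alpha or beta] diagnosis by HPLC, PCR or gene" mutation: both types enter.
- **Objective (Secondary Objectives, item 3).** "To study the association between resveratrol and changes in HbF levels". No type is named.
- **Allocation (Study Intervention).** Three groups, 1:1:1, stratified "based on gender (male and female) and serum ferritin". Thalassemia type is not a factor.
- **Analysis (Statistical Analysis).** "All patients who receive at least 1-time study drug will be analyzed in an Intention-to-treat" analysis, and "secondary outcomes [continuous variable] will be analyzed using Friedman's analysis of" variance. Neither statement separates or adjusts for type, or adjusts for baseline.
- **Size (Sample Size Calculation).** 20 per group, set for serum ferritin. There is no HbF effect size, SD or power, and no expected mix of alpha and beta patients.

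**The concern.** The objective is broader than the evidence cited for it. Patients for whom the protocol gives a reason to expect an HbF response are averaged with patients for whom it gives none. If the second group responds little or not at all, the pooled mean difference shrinks towards zero.

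A null pooled result would then be hard to read: it could mean no effect, or an effect confined to beta patients. A beta-only analysis added after unblinding would look data-driven. Because type is not a stratification factor, the arms can also differ in their mix by chance, which adds noise with 20 patients per arm.

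**Working it through.** **The plan's own figure.** None exists for HbF. The 20 per group is read from Table 1 of the protocol (small standardized difference, 80% column) for serum ferritin. It is used here only as the arm size.

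**Assumptions, not in the protocol.** Alpha share p; HbF effect d = 0.8 SD in beta patients; effect r × d in alpha patients, with r = 0 at first; within-type SD of 1 in both types; two-sample t-test, two-sided 5%, resveratrol against placebo.

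**Step 1: power when alpha patients do not respond.** The pooled mean difference is (1 − p)d with 20 per arm. Mixing responders and non-responders adds variance p(1 − p)d² in the resveratrol arm, so the averaged SD is √{[2 + p(1 − p)d²]/2}. The beta-only difference is d with 20(1 − p) per arm.

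For p = 0.3: pooled difference 0.7 × 0.8 = 0.56; SD = √[(2 + 0.21 × 0.64)/2] = 1.033; standardized difference 0.56/1.033 = 0.542.

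| Alpha share p | Pooled difference | Power, pooled | Beta patients per arm | Power, beta-only |
|---|---|---|---|---|
| 0.2 | 0.64 | 48.6% | 16 | 59.1% |
| 0.3 | 0.56 | 38.6% | 14 | 53.1% |
| 0.5 | 0.40 | 22.0% | 10 | 39.5% |

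Leaving out the mixing variance raises the pooled figures to 50.5%, 40.8% and 23.4%. With all 40 patients beta, power would be 69.3%.

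**Step 2: how small the alpha response must be.** Ignoring the mixing variance, the pooled signal-to-noise is proportional to (1 − p) + pr, and the beta-only one to √(1 − p). They are equal at r = [√(1 − p) − (1 − p)]/p:

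- p = 0.1: (0.949 − 0.900)/0.1 = 0.49
- p = 0.2: (0.894 − 0.800)/0.2 = 0.47
- p = 0.3: (0.837 − 0.700)/0.3 = 0.46
- p = 0.5: (0.707 − 0.500)/0.5 = 0.41

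Below these fractions of the beta effect, beta-only has more power. Above them, pooling does.

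**Step 3: sensitivity to the SD.** With r = 0 but an alpha SD one quarter of the beta SD, simulated pooled power is about 57%, 50% and 34% at p = 0.2, 0.3 and 0.5. The gap to beta-only (59%, 53%, 40%) falls to roughly 2, 3 and 6 points.

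**Step 4: chance imbalance.** With p = 0.3 and type left to chance (two independent binomials, 20 per arm), the two arms differ by four or more alpha patients with probability about 23%.

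**The case against.** The strongest reply is that the harm is conditional. The introduction reports where an HbF effect was seen; it does not say that alpha patients fail to respond. A reader might infer that pooling does dilute the effect and lower power, or that a beta-only analysis is better at any alpha share. The protocol supports neither. Both need a clearly smaller alpha response, and a material loss also needs a material alpha share; neither is given. Step 2 shows that pooling wins once alpha patients show about 41–49% of the beta effect, and Step 3 shows that the gap is small if alpha patients vary less. This part of the objection stands.

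It can also be said that by-type analyses of an unpowered secondary outcome belong in the SAP, which is not at hand, and that the all-treated population is a general definition that does not bar one. That is fair: an SAP with a by-type HbF analysis would meet most of the point. But the protocol does fix an objective, a population and a test, and together these pool the types.

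Lastly, the power figures are for a t-test, not for the planned Friedman test, so they do not measure the loss under the stated method. That is true. But Friedman's test, applied to a patient's repeated visits, ranks within patients and does not compare resveratrol with placebo, so it is no better basis for this objective.

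**Conclusion.** The mismatch is real: a beta-only rationale, a mixed population, an unrestricted objective, and neither stratification nor analysis by type. That pooling harms the HbF result is a possibility, not a demonstrated fact. If alpha patients do not respond, SDs are equal and the beta effect is 0.8 SD, the loss against a beta-only analysis is about 11 points of power at a 20% alpha share (59.1 − 48.6), 15 at 30% (53.1 − 38.6) and 18 at 50% (39.5 − 22.0). It is much smaller if alpha patients vary less, and it reverses if they show about half the beta effect or more.

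No stated power figure is contradicted, because none exists for HbF. Even beta-only power is 40–59% in these scenarios, so HbF stays exploratory either way. The point is minor. It is worth acting on because the remedy is cheap and makes a null or positive HbF result interpretable.

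**What to change.** Analyse objective 3 as resveratrol against placebo by ANCOVA of month-6 HbF, adjusted for baseline HbF and thalassemia type. The type term deals with chance imbalance but does not undo dilution. So also pre-specify, before unblinding, a beta-thalassemia estimate reported alongside the all-patient estimate. The alternative to that beta estimate is to state why an HbF effect is expected in alpha patients. Making beta patients the sole main population is debatable on what the protocol gives, and is not needed.

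The cost is a few lines in the protocol or SAP and one extra analysis. Type is known from the eligibility diagnosis, and Hb typing is already among the visit tests, so no patients, visits or samples are added. The downside is lower precision in the beta-only estimate.

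### The entry exclusion names omeprazole alone, although the rationale, planning effect and discontinuation criterion concern proton pump inhibitors as a class

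*Protocol*

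**What the plan says.** Under Exclusion Criteria, the only criterion about medicines in current use is "Currently receive omeprazole or resveratrol". The nearest other exclusion, "Chronic inflammation or other conditions that might confound serum ferritin" interpretation, concerns conditions rather than medicines. The protocol gives no washout and no list of prohibited acid suppressants. The background treatment described under Study Intervention ("All groups will receive standard treatments including iron chelators, folic acid" and other supplements) does not mention them. Randomisation is stratified by gender and serum ferritin only.

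Three other places work at class level:

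- The background text gives the mechanism as general: "agents/compounds that reduce gastric acidity may decrease iron" absorption. It adds that previous studies "have demonstrated the use of PPIs, including pantoprazole and esomeprazole, in managing iron" overload.
- Sample Size Calculation takes its planning effect, "Expected standardized difference of 0.22", from a trial of pantoprazole added to chelators.
- Discontinuation Criteria lists "Have indication for proton pump inhibitor or resveratrol such as gastrointestinal bleeding".

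Under Statistical Analysis, the intention-to-treat set is everyone who took at least one dose of study drug. The per-protocol set is those who received at least 80% of it.

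**The concern.** If pantoprazole is close enough to omeprazole to supply the planning effect, a pantoprazole user on placebo already has the mechanism under test, and one given omeprazole has less to gain from it. Either patient pulls the omeprazole-placebo difference towards zero.

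The entry and discontinuation lists also differ in scope. Entry is decided by one named drug, and discontinuation by an indication for the class. A patient with a standing PPI indication who takes something other than omeprazole passes the first list and may already meet the second. What is at stake is the size of the omeprazole-placebo contrast, or the loss of randomised patients who could have been screened out.

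**Working it through.** **Scope, side by side.**

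| Place in protocol | Scope |
|---|---|
| Background, mechanism | Any agent lowering gastric acidity |
| Background, evidence | PPIs, including pantoprazole and esomeprazole |
| Sample Size Calculation | Pantoprazole trial |
| Exclusion Criteria | Omeprazole (and resveratrol) |
| Discontinuation Criteria | Indication for any PPI (or resveratrol) |

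Only the exclusion is at single-drug level.

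**What happens to a pantoprazole user.** The outcome depends on how the discontinuation criterion is read.

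- If it covers only indications that arise on study, the patient stays and contributes an attenuated difference.
- If it also covers an indication present at entry, the patient is stopped after randomisation. After one dose the patient remains in the intention-to-treat set with little exposure, and drops out of the per-protocol set if under 80% of study drug was received.

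The same patient cannot suffer both.

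**The plan's own figures.** The two falls in ferritin quoted from the pantoprazole trial are 1444 − 1197 = 247 and 1928 − 1501 = 427 ng/mL, which differ by 180. Which arm had the larger fall does not enter this check. With the root mean square of the standard deviations 613 and 956, √[(613² + 956²)/2] = 803, the standardized difference is 180/803 = 0.224, which reproduces the stated 0.22. The 20 per group is read from the protocol's Table 1 (small effect, 80% power). A two-sided two-mean formula does not reproduce it: 2(1.960 + 0.842)²/0.22² gives 325 per arm. That is a separate matter, noted only because it sets the scale of the last two columns below.

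**Dilution.** Let Δ be the omeprazole effect in non-users, c the share of each arm on another PPI, and g the fraction of Δ that a user still gains from added omeprazole (0 ≤ g ≤ 1). Then

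expected difference = (1 − c)Δ + c·g·Δ = Δ[1 − c(1 − g)].

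The worst case, g = 0, means the other PPI is equally effective and omeprazole adds nothing. The difference is then (1 − c)Δ. With the variance unchanged, information is (1 − c)² and the required sample size is multiplied by 1/(1 − c)². The documents do not give c; 5% to 20% is assumed.

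| c | Patients per arm of 20 | Difference, g = 0 | Standardized | Information | n multiplier | Power at 325 per arm | Power at 20 per arm |
|---|---|---|---|---|---|---|---|
| 0 | 0 | 1.00 | 0.220 | 1.00 | 1.00 | 80% | 10.3% |
| 5% | 1 | 0.95 | 0.209 | 0.90 | 1.11 | 76% | 9.7% |
| 10% | 2 | 0.90 | 0.198 | 0.81 | 1.23 | 71% | 9.1% |
| 20% | 4 | 0.80 | 0.176 | 0.64 | 1.56 | 61% | 8.0% |

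Power is Φ(δ√(n/2) − 1.960), where δ is the diluted standardized difference.

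If users kept half the gain (g = 0.5, for illustration), the same three shares would give 1 − 0.05 × 0.5 = 0.975, 1 − 0.10 × 0.5 = 0.95 and 1 − 0.20 × 0.5 = 0.90. The g = 0 rows are therefore the largest dilution for each c.

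**The case against.** The protocol does contain a class-wide PPI rule. An investigator who knows the discontinuation criterion would have little reason to enrol a patient with a standing PPI indication, so few such patients may enter. This stands as a reason to expect a small share. It does not close the gap: the rule acts after enrolment, turns on an indication rather than on use, and leaves any treated patient in the intention-to-treat set. Eligibility should not depend on investigators anticipating a later list.

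A reader might infer that a pantoprazole user both dilutes the contrast and is discontinued at once. The documents do not support that. These are alternatives, and the example of gastrointestinal bleeding leans towards new events, under which immediate discontinuation would not follow.

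A reader might also take the 36% loss of information at c = 20% as an expected result. Nothing in the protocol ties any share to these outpatients, and the figure needs an equal effect and no added gain. At 20 per group, even that case moves power only from 10.3% to 8.0%, so sample size limits this trial far more. This objection stands on size but not on direction.

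The harm is attenuation. Randomisation still protects the comparison under the null, and the mechanism does not dilute resveratrol against placebo in the same way. Finally, history taking is a scheduled activity, and a medication form or sensitivity analysis may exist in documents not shown, so their absence is not part of this point.

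**Conclusion.** The mismatch is certain from the text: the exclusion is narrower than the rationale, the planning effect and the discontinuation criterion, and it admits users of other PPIs to any arm. The consequence is conditional. It is either attenuation of the omeprazole-placebo difference or avoidable withdrawal after randomisation, depending on how the discontinuation criterion is applied.

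For an assumed share of 5% to 20% per arm, the difference would fall to no less than 0.95 to 0.80 of its value. This assumes equal shares in the two arms and is the worst case for each share. Confidence is high for the wording gap and limited for its size, because the share is unknown. The change is worth making because it costs little. The gap does not invalidate the trial.

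**What to change.** Reword the exclusion to cover current use of any PPI, alongside resveratrol, and reconcile it with the class-level discontinuation criterion. The protocol should state whether that criterion includes an indication already present at entry.

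Extending the exclusion to other regular acid suppressants is optional. It rests only on the general mechanism sentence in the background, and it would go beyond the discontinuation criterion, which names only PPIs and resveratrol.

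If enrolment has begun (the stated study window opens on 10 February 2025), record acid-suppressant use at baseline and at the 3- and 6-month visits. Add a sensitivity analysis that leaves out patients who were users at baseline. Define that exclusion by baseline use only, because use that starts after randomisation may itself depend on treatment.

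The cost is a slightly smaller eligible pool and an amendment to an ethics-approved protocol.

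### The protocol does not say whether patients discontinued for needing more chelator keep their ferritin follow-up, so the announced intention-to-treat analysis may shrink to completers partly selected on iron control

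*Protocol*

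**What the plan says.** - **Protocol, Discontinuation Criteria.** The list includes "Need to increase the dose of iron chelation while currently in study" and "Protocol violations that significantly affect data collection or interpretation". A separate item reads "Have conditions that are not suitable for continuation of study". No item says whether study drug, study visits or both come to an end, and no item says that the patient leaves the analysis.
- **Protocol, Research Design.** Blood, including ferritin, is taken at the first visit, at 3 months and at 6 months. Nothing is said about sampling after a patient has been discontinued.
- **Protocol, Statistical Analysis.** The main set is defined by "All patients who receive at least 1-time study drug will be analyzed in an Intention-to-treat". A second set is defined by "Patients who receive at least 80% of the study drug will be analyzed in a Per-protocol". The primary outcome "will be analyzed using Friedman's analysis of" variance.
- **Protocol, Inclusion Criteria.** Chelator dose must have been stable for 3 months, with no change expected during the study. Patients with ferritin above 1000 ng/mL must already be on the maximum chelator dose.
- **Grade 3 or higher events.** The discontinuation list has "Have more or equal than grade 3 adverse events", while Research Design says that "doctors may decrease the dosage of the study drug according to the following table", which implies that the patient continues. These two passages must be reconciled. They also show that the protocol does not use discontinuation with one fixed meaning.

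**The concern.** Chelators are the treatment for iron overload, ferritin is the primary outcome, and ferritin is measured at month 3. A patient judged at that visit to need more chelator is plausibly one whose iron control is poor. If follow-up stops there, the month-6 value is missing for a reason linked to the outcome. If the adjunct works, this would happen more often on placebo. Dropping these patients would make placebo look better than it is and pull the comparison toward no effect.

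A SAP can choose how to handle missing values, but it cannot recover a ferritin that was never drawn. Whether visits continue after study drug stops therefore has to be settled in the protocol while patients are still being seen.

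**Working it through.** **1. What follows from the text**

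- *Who is discontinued:* among others, patients needing more chelator and patients with violations that affect the data.
- *What they discontinue:* not stated for either group. The reference to continuing in the study stands in a different item.
- *What is measured afterwards:* not stated.
- *Who is analysed:* everyone with at least one dose.
- *How:* Friedman's test. With the patient as block and the three visits as repeated measurements, a patient without a month-6 value is an incomplete block and drops out.

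So if visits continue, the promised set can be analysed. If they stop, the analysis reduces to completers whatever the set is called. The protocol permits either reading.

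**2. How large could the effect be?**

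The protocol gives no figure for escalation, so there is nothing to reproduce. The only planning figures are a standardized difference of 0.22 and 20 patients per group (Sample Size Calculation). Everything else below is assumed:

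- change in ferritin in SD units (SD 1 at both visits, bivariate normal, higher is worse);
- placebo mean 0; active mean −d/2 at month 3 and −d at month 6;
- correlation r between month-3 and month-6 change of 0.5 or 0.8;
- patients lost if month-3 change exceeds a cut-off c, set so that a share p of placebo (5, 10 or 20%) is lost;
- true d of 0.22 (protocol) or 0.50 (for range).

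With φ and Φ the standard normal density and distribution function, and λ(x) = φ(x)/Φ(x):

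- share of active lost = 1 − Φ(c + d/2)
- difference among completers = d − r·[λ(c) − λ(c + d/2)]

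Example with d = 0.22, r = 0.8, p = 20%: c = 0.8416, λ(c) = 0.3500, λ(c + 0.11) = 0.3059. The difference is 0.22 − 0.8 × (0.3500 − 0.3059) = 0.185, an attenuation of 16%.

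| r | Placebo lost | Active lost, d = 0.22 | Completer difference | Attenuation | Active lost, d = 0.50 | Completer difference | Attenuation |
|---|---|---|---|---|---|---|---|
| 0.5 | 5% | 4.0% | 0.210 | 4.4% | 2.9% | 0.480 | 4.0% |
| 0.5 | 10% | 8.2% | 0.205 | 6.8% | 6.3% | 0.468 | 6.3% |
| 0.5 | 20% | 17.1% | 0.198 | 10.0% | 13.8% | 0.452 | 9.5% |
| 0.8 | 5% | 4.0% | 0.204 | 7.1% | 2.9% | 0.468 | 6.5% |
| 0.8 | 10% | 8.2% | 0.196 | 10.9% | 6.3% | 0.449 | 10.1% |
| 0.8 | 20% | 17.1% | 0.185 | 16.0% | 13.8% | 0.424 | 15.2% |

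A second assumed model gives much the same. It uses log-ferritin change with SD 0.3, month-3 cut-offs of 0.2 to 0.4, true effects of 0.15 or 0.30, and correlation 0.5 or 0.7. It loses 9 to 25% of placebo and 3 to 18% of active patients, with attenuation of 5 to 15%.

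**3. Against the trial's precision**

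The standard error of a difference between two arms of 20, in SD units, is √(2/20) = 0.316. At d = 0.22 the bias is 0.010 to 0.035 SD, or 0.03 to 0.11 standard errors. At d = 0.50 it is 0.020 to 0.076 SD, or 0.06 to 0.24 standard errors.

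**The case against.** A reader might infer that the protocol removes these patients, so that its intention-to-treat analysis is a completer analysis in disguise and contradicts its own label. The text does not support that.

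- The criteria concern discontinuation, not exclusion from analysis. The wording about continuing in the study cannot be carried over to the chelation or violation items.
- Protocol violators who took at least one dose are already in the intention-to-treat set by its definition. Nothing excludes them; only their follow-up is unclear.
- No ferritin trigger for a chelator increase is stated, so calling the criterion driven by rising ferritin is interpretation. The entry rules make escalation less likely: the dose must be stable with no change expected, and patients above 1000 ng/mL are already at the maximum dose. The calculation above ignores this.
- The attenuation rests on assumed inputs, and on a between-arm difference in means that the protocol does not name as its analysis. Friedman's test across visits compares visits within patients, which is a separate problem.
- In that model the loss depends only on the observed month-3 value. A likelihood-based repeated-measures analysis using that value would avoid the bias, so the complete-block test is part of the cause.
- Methods for missing data and sensitivity analyses may stand in a SAP that is not shown. Their absence is no finding.

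All of this stands and limits the claim. It does not remove the gap: an outcome-related discontinuation criterion, no stated ferritin follow-up after it, and a primary test that cannot use a patient without month 6.

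**Conclusion.** The point holds as an ambiguity with a plausible bias, not as a demonstrated contradiction. Read one way, the plan keeps every dosed patient. Read the other way, it analyses completers partly selected on iron control. Under the second reading the likely direction is toward no effect, so a false claim of efficacy is not the main worry.

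The protocol supports no estimate of frequency or size. The hypothetical attenuation of roughly 4 to 16% assumes that escalation follows month-3 ferritin, that half of the effect is present by then, and that 5 to 20% of placebo patients (1 to 4 of 20) are affected. At the planned effect, that bias is small beside sampling error. The reason to act is that the remedy is cheap now, whereas unmeasured month-6 values cannot be recovered later.

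**What to change.** Leave the clinical stopping rules to the investigators and amend the text around them:

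1. State that meeting a discontinuation criterion stops study drug only. Except on withdrawal of consent, patients keep the month-3 and month-6 ferritin measurements.
2. Record every chelator change with its date and dose.
3. State that these patients, violators included, stay in the primary intention-to-treat analysis.
4. For the primary comparison, name a between-group method that keeps patients with incomplete visits, for example a repeated-measures model adjusted for baseline ferritin.
5. Reconcile the two passages on grade 3 or higher events, so that it is clear what discontinuation means.

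A sensitivity analysis for chelator escalation, such as ranking those patients as worst outcomes, is optional.

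The cost is amendment wording and visits at the same clinic. The downside is that ferritin after an escalation partly reflects the added chelator, so recording the changes matters and the optional sensitivity analysis would help.
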